## Executive Summary

Physical inactivity increases the risk for multiple chronic diseases, early mortality, and accelerated cognitive decline in aging adults. Interventions to enhance physical activity among older adults are needed to improve health outcomes and reduce the burden on healthcare systems. We propose a remotely administered behavioural intervention that uses social motivation manipulation, and self-transcendence messages to effectively enhance physical activity in older adults. This randomized controlled trial consists of daily messaging delivered via smart-phone over 4 weeks in 120 healthy but 'at risk' older adults over the age of 60 years from the PResymptomatic EValuation of Experimental or Novel Treatments for AD (PREVENT-AD) cohort. Participants are randomly assigned to one of two groups: an intervention group, who are recruited with a child or grandchild (14 years or older) and receive socially motivating feedback, and an active control group, who are recruited without a family member. The primary outcome is the change in physical activity as measured by accelerometers following the intervention compared to a pre-intervention baseline. Recruitment takes place among current participants of the PREVENT-AD cohort as an optional sub-study. These participants have already undergone MRI and Alzheimer's disease biomarker assessment as part of the PREVENT-AD cohort. During the present sub-study, these participants will be assessed remotely using telephone/videoconference and computerized neuropsychological tests, computerized behavioural measures, and psychosocial surveys at baseline and after the intervention. Assessment of cognition, affect and fitness will serve as secondary outcome measures. Participants in each group will be offered the opportunity to participate in a cross-over second period of the study, to ensure that participants in the active control group have access to a potentially beneficial intervention and to serve as a longer-term follow-up of both groups. This study will assess the effectiveness of a novel behavioural intervention at enhancing physical activity in older adults and examine the neurobehavioural mechanisms underlying any such behavioural change.

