## 4. Methods/Assessments

### 4.1 Overview

In 120 sedentary and cognitively asymptomatic older adults (60 years and older) we will test whether a behavioural intervention combining social motivation, and self-transcendence messages decreases the amount of time participants are sedentary, as measured by accelerometry. We will use a stratified randomization scheme to ensure that half of the participants in each group will be randomized and stratified by their risk of developing Alzheimer's disease: to the social motivation + self-transcendence messaging (intervention) and the other half will be randomized to a daily activity monitoring group (active control). Participants will not be explicitly told to exercise as part of the study, but during the experiment they will receive messages that encourage walking or decreasing sedentary time. The primary measure of interest is decrease in sedentary behavior. All participants will be recruited from the PREVENT-AD cohort (STOP-AD Centre) at the Douglas Mental Health University Centre. Participants will be screened remotely by researchers affiliated with McGill University under the direction of [name].

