To test our main hypothesis that social motivation + self-transcendence messaging + home-based physical training will produce the largest increase in physical activity over the course of the 4-week intervention compared to the active control, we will perform repeated measures ANCOVAs (with group as a between-subject factor and pre-post session as a within-subject factor). This hypothesis will be examined by analyzing total number of steps and percent time sedentary. We will analyze structural/functional MRI connectivity to test the hypothesis that increased physical activity following the intervention is associated with enhanced brain connectivity between brain regions in reward valuation (i.e., ventral tegmental area and ventral striatum) and social processing (vmPFC). We will conduct seed-based functional connectivity analyses using methods as in our prior research [9, 29-31]. To mitigate the influence of motion, we will identify and address artifactual motion outliers in data modeling, and employ quality assurance software to mitigate head motion artifacts and physiological aliasing ([https://www.nitrc.org/projects/artifact\\_detect](https://www.nitrc.org/projects/artifact_detect)). We will control for the effects of demographic variables (e.g., age, sex, education, diet, mood, socioeconomic status, alcohol, vascular risk factors and sleep). We apply a whole-brain height threshold of  $p < 0.001$  ( $T = 3.24$ ) and false discovery rate cluster threshold of  $p < 0.05$ . We will examine brain modularity, which indexes the segregation between networks, and has previously been shown to predict cognitive gains after a physical exercise intervention [20]. In addition to these hypothesis-driven analyses, we will perform an agnostic, data driven multi-voxel pattern analysis of resting-state data using an approach published by our collaborator [21].

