Cover Page

Statistical Design and Power

Study Title: The Healthy Aging Brain Study: A Remote Behavioral Intervention to Enhance Physical Activity in Older Adults.

Document creation date: March 7th, 2023

Statistical Design and Power

We will recruit 60 older adults over 60 years old (30 Intervention Group, 30 Control Group) from the PREVENT-AD cohort. This sample size was determined using power calculations that will allow us to identify a minimum detectable difference of 10.0%, with a common standard deviation of 14.0% (estimated from a similar physical activity intervention) with 80% power and a two-sided alpha of 0.05. Our research goal is to identify the neurobehavioral mechanisms underlying physical activity engagement in at-risk older adults and test the efficacy of a scalable, technology-based intergenerational behavior intervention on physical activity engagement. Our planned analyses and anticipated results for each Specific Aim are outlined below:

Aim 1) We will apply linear mixed effect models to determine the extent to which intergenerational social motivation enhances physical activity (primary outcome) and secondary outcomes (cognition, loneliness, self-efficacy, mood, and sleep) in at-risk older adults within the Intervention compared to the Control Group. Demographic variables (age, sex, socioeconomic status, neighborhood walkability) and AD multimodal risk score will be included as covariates of non-interest.

Aim 2) We will apply the NIH Science of Behavior Change theoretical framework to determine whether target mechanisms (social support, generativity or reward sensitivity) separately mediate the influence of the intervention on physical activity engagement. This approach will provide novel insights about target, potentially modifiable mechanisms that mediate successful behavior change in older adults at risk for AD.

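### The imaging height threshold pairs p < 0.001 with T = 3.24, which holds only one-sided at 56 to 58 residual df: not at the protocol's 120, nor at 60 with the listed covariates

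*Protocol*

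**What the plan says.** The threshold appears once, in Protocol section 6b. The sentence begins "We apply a whole-brain height threshold of" p < 0.001, puts T in brackets, and continues "T = 3.24$ ) and false discovery rate cluster threshold of" p < 0.05. It gives no residual df, no sidedness and no number of participants with usable imaging.

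The sentence just before it describes the adjustment: "We will control for the effects of demographic variables (e.g., age, sex, education, diet, mood, socioeconomic status, alcohol, vascular risk factors and sleep". Later in section 6b the resting-state and task fMRI analyses are called secondary and assigned to a general linear model.

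The two documents give different sample sizes. Protocol section 4.1 has "In 120 sedentary and cognitively asymptomatic older adults (60 years and older", and the Executive Summary agrees: "120 healthy but 'at risk' older adults over the age of 60 years". The SAP has "We will recruit 60 older adults over 60 years old (30 Intervention Group, 30 Control Group".

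On direction, the imaging hypothesis in section 6b is directional: more activity goes with enhanced connectivity. Hypothesis 3 in Protocol section 2 says only that baseline connectivity will predict change in activity, without a sign.

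**The concern.** A T cut-off stands for a p value only once the residual df and the sidedness are fixed. Printing both numbers as equivalent therefore commits the plan to a particular design, here one-sided with about 57 df. The protocol's own sample of 120 does not give that df. Neither does a sample of 60 once the adjustment in the preceding sentence is made.

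The height threshold decides which clusters form before the FDR step. If T and p disagree in the model actually fitted, an analyst could apply either one and claim to have followed the protocol. One fixed T also cannot serve models with different df, and section 6b plans several: resting-state and task data, intervention effects, and prediction of change.

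**Working it through.** **Inputs.** T = 3.24 and p = 0.001 from Protocol section 6b; n = 120 from Protocol section 4.1; n = 60 from the SAP; nine example covariates from section 6b.

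**Assumptions.** Every enrolled participant contributes imaging. Each model has an intercept and one regressor of interest (2 parameters), or these plus nine single-df covariates (11 parameters). The documents state none of this.

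**Formulas.** Residual df = n − number of parameters. The critical T for p = 0.001 is the 0.999 quantile of Student's t (one-sided) or the 0.9995 quantile (two-sided). The p value at T = 3.24 is the upper tail area beyond 3.24, doubled for two-sided.

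**Step 1: reproduce the plan's figure.** One-sided critical values:
- 55 df: 3.2451
- 56 df: 3.2423
- 57 df: 3.2395
- 58 df: 3.2368
- 59 df: 3.2342

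Only 56, 57 and 58 df round to 3.24. Two-sided, the critical value falls towards 3.2905 as df grows without limit, so it cannot be 3.24 at any df.

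**Step 2: compare with the documented sample sizes.**

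| n | parameters | df | one-sided T | two-sided T | one-sided p at 3.24 | two-sided p at 3.24 |
|---|---|---|---|---|---|---|
| 60 | 2 | 60 − 2 = 58 | 3.237 | 3.466 | 0.00099 | 0.0020 |
| 60 | 11 | 60 − 11 = 49 | 3.265 | 3.500 | 0.00108 | 0.0022 |
| 120 | 2 | 120 − 2 = 118 | 3.161 | 3.375 | 0.00078 | 0.0016 |
| 120 | 11 | 120 − 11 = 109 | 3.167 | 3.382 | 0.00079 | 0.0016 |

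Only the first row, one-sided, reproduces 3.24.

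**Step 3: which other designs would reproduce it.** With 11 parameters, 56 to 58 df needs 56 + 11 = 67 to 58 + 11 = 69 participants with imaging. That could be a subset of 120, but the documents do not say so.

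**The case against.** The strongest reply is that T and p can both hold. Sixty participants less two parameters gives 58 df, and the one-sided cut-off is then 3.24. Sixty is the SAP's own sample size, and the section 6b imaging hypothesis is directional, so a one-sided threshold would suit it. This stands. A reader might infer from the mismatch at 120 that the pair is impossible; the documents do not support that. The mismatch at 120 partly reflects the separate disagreement between protocol and SAP on sample size.

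A reader might also infer that the imaging test is meant to be two-sided, because the SAP specifies "80% power and a two-sided alpha of 0.05". That phrase belongs to the sample-size calculation for physical activity and says nothing about voxel-wise tests. Sidedness for imaging is unstated, which is a gap and not a contradiction.

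The covariate list opens with an example marker, so neither the number of terms nor their df is fixed, and 67 to 69 scans with 11 parameters would also give 3.24. This stands too, and is why the 109 and 49 df figures are labelled as assumptions.

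Finally, error control is applied at cluster level by the FDR step, so a change of 0.03 to 0.07 in T does not multiply the reported error rate. That is fair, and it limits the consequence. A larger inflation could be obtained by imagining a covariate-adjusted model within one arm, but no such analysis is planned.

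What the reply leaves untouched is that the only match at a documented sample size requires the smaller sample and no covariates, while section 6b says covariates will be controlled.

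**Conclusion.** The point holds as a minor inconsistency. T = 3.24 is the one-sided 0.001 cut-off at 56 to 58 residual df. It fits the SAP's 60 participants without covariates. It does not fit the protocol's 120 with or without the nine covariates, or 60 with them.

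One-sided, the effect is negligible: p is about 0.0008 at 109 df, slightly stricter than stated, and 0.0011 at 49 df, slightly looser. If both signs are examined at the same cut-off, voxel-level p is about 0.0016 to 0.0022, or 1.6 to 2.2 times the stated 0.001. That second range applies only where no direction is specified, as in hypothesis 3.

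All of these figures assume that everyone enrolled has usable imaging and that each covariate costs one df. The analyses concerned are secondary, and the primary activity outcomes are not affected.

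**What to change.** In Protocol section 6b, delete the fixed T value. Keep the voxel-level threshold p < 0.001, with T computed from each model's actual residual df. State sidedness for each imaging hypothesis: one-sided where a direction is given, two-sided where it is not. Then apply the cluster FDR of 0.05 as now.

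The cost is one sentence and no new data. For one-sided contrasts the cut-off hardly moves (3.17 at 109 df, 3.27 at 49 df, against 3.24). The downside is a slightly stricter cut-off for two-sided contrasts: 3.38 at 109 df or 3.50 at 49 df, under the same assumptions as above.

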## 5.6. Cross-over design

In order to ensure that participants in the active control group have the opportunity to enroll in the intervention, a cross over period 2 is in place. Enrolled participants who complete the first period of the study will be offered the possibility to participate in a follow-up assessment to ascertain a maintenance effect. While the primary endpoint is at the completion of period 1 for all participants, an identical schedule of acquisition is implemented for period 2. Both groups are offered the opportunity to crossover into the other arm of the study (intervention to active control; active control to intervention). This follow-up will consist in a cross-over to the opposite study arm to which they were initially randomized. The study will include two periods of 4 weeks separated by a washout period of at least 6 weeks.

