#### 6b Data analysis

Outcome measures outside of the neuropsychological assessment battery are as follows:

Outcome measure	Type	Timeframe	Brief description
Total step count (average steps/day)	Primary	Week 0 (baseline); Week 2; Week 4.	This metric quantifies the change in the average number of steps taken each day, from the baseline, Week 2, and Week 4. It is a marker of change in habitual ambulatory activity.
Sedentary behavior (average min/day)	Primary	Week 0 (baseline); Week 2; Week 4.	This metric quantifies the change in the average amount of time spent sedentary each day, from the baseline, Week 2, and Week 4.

			2, and Week 4. It is a marker of time spent inactive.
Moderate-vigorous activity (average min/day)	Secondary	Week 0 (baseline); Week 2; Week 4.	This metric quantifies the change in the average amount of time spent engaged in moderate-to-vigorous physical activity each day, from the baseline, Week 2, and Week 4. It is a marker of physical activity.
Walking Cadence	Secondary	Week 0 (baseline); Week 2; Week 4	This metric reflects the participant's average steps per minute. We will examine change from baseline over the course of the intervention.
Walking Bouts	Secondary	Week 0 (baseline); Week 2; Week 4	This measures the number of 'bouts' of physical activity (in our case, steps). We will have two counts: the number of 5+ minute bouts and the number of 10+ minute bouts of walking. We will examine changes from baseline over the course of the intervention.

A spreadsheet holding the list of neuropsychological assessments to be used, with brief descriptions, is attached. They will be administered at T1 (Week 0), T2 (Week 1), and T3 (Week 4).

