After compiling all data across the 3 different data servers, data will be checked for completeness and correctness using frequency distributions (for missing data and out-of-range A-B values). Group differences at baseline are examined for variables including demographic factors (i.e., age, sex, educational level, socioeconomic status, culture), baseline sedentary time, self-report sitting time, and estimated fitness, in order to detect potential confounding factors. For the primary hypothesis that social motivation + self-transcendence messages decrease sedentary time more than an active control, all outcome measures about sedentary behaviour are first quantified using available software. Changes in sedentary behaviour (% daily sitting and lying time, minutes/per day in physical activity, count of steps) over time (3-time points) are analyzed using linear mixed effect models to account for the correlated data and likely heterogeneous variability.

Non-linear changes across 3-time points are also examined by including quadratic effects. These models will include a random intercept and slope to account for subject-specific changes as well as a group (2) x time (3) interaction fixed effect. This allows for modelling of the effect of our intervention as a function of both groups and time as well as accounting for potentially confounding covariates. All model assumptions will be tested both visually and formally and associations between covariates will be assessed to protect against multicollinearity.

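### Linear random slope over weeks 0, 2 and 4: standard errors for week 2, and for the weeks 2/4 average, versus baseline are too small if participants differ in response and most of it appears early

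*Protocol*

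**What the plan says.** Protocol 6b states that changes in sedentary and activity measures "over time (3-time points) are analyzed using linear mixed effect models to account for the correlated data and likely heterogeneous variability". It adds that "Non-linear changes across 3-time points are also examined by including quadratic effects", and then gives the structure: "These models will include a random intercept and slope to account for subject-specific changes as well as a group (2) x time (3) interaction". It does not say whether time is a factor or continuous, what scale the slope uses, what the residual covariance is, or which contrast carries the efficacy claim.

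The outcome table in 6b lists weeks 0, 2 and 4 for both primary outcomes; for steps it describes "the change in the average number of steps taken each day, from the baseline, Week 2, and Week 4". Protocol 5.6 (Cross-over design) fixes the endpoint more narrowly: "While the primary endpoint is at the completion of period 1 for all participants". For the same hypothesis, 6b also says "we will perform repeated measures ANCOVAs (with group as a between-subject factor and pre-post session as a within-subject factor". The SAP names the model class only: "We will apply linear mixed effect models to determine the extent to which intergenerational social motivation enhances physical activity (primary outcome". It gives no covariance structure.

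**The concern.** Week 0 precedes the intervention, while weeks 2 and 4 both fall within it. A participant who responds promptly shows a step between week 0 and week 2, then a plateau. A linear random slope has a different shape: each person's deviation at week 2 is half of that at week 4. If people differ in response and the response comes early, intercept plus slope cannot reproduce the covariance of the three visits. Standard errors then go wrong in a direction that depends on the contrast.

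Differences in response are what the trial expects. Aim 2 looks for moderators of behaviour change, and Aim 3 for predictors of it.

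The quadratic terms raise a smaller question. Three time points carry two degrees of freedom for time, and a three-level factor with its group interaction already uses both.

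**Working it through.** **The plan's own figure.** The documents give no standard error or variance component for this model. The only related figure is the SAP sample size of 30 per arm (difference 10%, SD 14%, 80% power, two-sided 0.05). The normal formula gives 2 × (1.960 + 0.842)² × 14² / 10² = 30.8, so 31 per arm; power at 30 per arm is 0.79. That agrees to rounding. The conflict between 60 participants (SAP) and 120 (Protocol) does not change the ratios below, because sample size cancels.

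**Quadratic terms.** With time as a three-level factor crossed with group, the design has 6 columns and rank 6. Adding t² and group × t² gives 8 columns and still rank 6, so the added terms are aliased. With continuous time, linear plus quadratic by group is the same saturated three-point mean model, and nothing is redundant.

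**Set-up for the slope (assumptions).** Let Y0 = b + e0, Y2 = b + p·s + e2 and Y4 = b + s + e4. Here s is the person-specific response, with variance vs; p is the share of it present by week 2; and the residual variance is ve. A pure step has p = 1 and linear growth has p = 0.5. I assume intercept variance 0.6, ve = 0.2 and vs = 0.2 to 0.4.

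**What the fitted model implies.** With complete, balanced data, intercept plus linear slope reproduces the variance of the week 4 minus week 0 difference and that of the curvature contrast (1, −2, 1). It forces the covariance between them to zero. The variances per participant are therefore:

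| Contrast | Model | True |
|---|---|---|
| Week 2 − week 0 | vs[1 + (1−2p)²]/4 + 2ve | p²vs + 2ve |
| Mean of weeks 2, 4 − week 0 | vs[9 + (1−2p)²]/16 + 1.5ve | vs(1+p)²/4 + 1.5ve |
| Week 4 − week 0 | vs + 2ve | vs + 2ve |
| Week 4 − week 2 | vs[1 + (1−2p)²]/4 + 2ve | (1−p)²vs + 2ve |

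The SE ratio is √(model/true), and type I error is 2 × P(Z > 1.96 × ratio).

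**Pure step (p = 1), vs = 0.2 to 0.4.**
- Week 2 vs baseline: √(0.5/0.6) = 0.913 to √(0.6/0.8) = 0.866; type I error 7.4% to 9.0%.
- Weeks 2/4 average vs baseline: √(0.425/0.5) = 0.922 to √(0.55/0.7) = 0.886; 7.1% to 8.2%.
- Week 4 vs baseline: ratio 1.000; 5.0%.
- Week 4 vs week 2: √(0.5/0.4) = 1.118 to √(0.6/0.4) = 1.225; 2.8% to 1.6%.
- Two-degree-of-freedom group × time test: 5.2% to 5.5%.

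**70% present by week 2 (p = 0.7).**
- Week 2 vs baseline: √(0.458/0.498) = 0.959 to √(0.516/0.596) = 0.930; 6.0% to 6.8%.
- Weeks 2/4 average vs baseline: √(0.4145/0.4445) = 0.966 to √(0.529/0.589) = 0.948; 5.8% to 6.3%.

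**Linear growth (p = 0.5), or a step common to everyone (vs = 0).** Every ratio is 1.

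**Simulation.** I took the pure step with other assumed variances (intercept 1, ve 0.25, vs 0.25 to 1, and one case with the varying step in the intervention arm only), at 30 and 60 per arm, with 20,000 null runs each. Fits at the boundary were replaced by compound symmetry.

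| Contrast | Type I error, planned structure |
|---|---|
| Week 2 vs baseline | 7.0% to 10.4% |
| Weeks 2/4 average vs baseline | 6.4% to 9.1% |
| Week 4 vs baseline | 4.7% to 5.1% |
| Week 4 vs week 2 | 0.5% to 3.0% |
| 2-df group × time | 4.6% to 5.5% |

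With an unstructured 3 × 3 covariance, every contrast lay between 4.6% and 5.3%.

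**The case against.** The strongest reply is that the tests the plan points to are sound. The only effect 6b names is the group by time interaction, whose joint test stays near 5%. Protocol 5.6 puts the primary endpoint at the end of period 1, which best matches week 4 versus baseline, and that standard error is right with complete data. This stands. A reader might infer that the main efficacy test has an inflated false-positive rate, or that all on-treatment comparisons have standard errors that are too small. The documents support neither reading, and week 4 versus week 2 errs on the conservative side.

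A second reply is that an early response is assumed. Messages run daily for four weeks and donations depend on weekly goals, so gradual growth is equally consistent with the text. That also stands, and it is why the conclusion is conditional. The text says only slope; linear is the ordinary meaning, but an inference.

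Third, a reader might infer that the quadratic makes the model inestimable. The (2) and (3) may simply count groups and time points. Under continuous time the quadratic is legitimate; under a factor, the aliased term leaves the fitted means unchanged.

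Fourth, 6b promises visual and formal checks of model assumptions. It names no alternative covariance to use if a check fails, so this answers the point only in part.

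What remains is that week 2 is in the timeframe of both primary outcomes and, with baseline as reference, is one of the two interaction coefficients. No mixed-model contrast is named as primary, so a week 2 or average effect could be reported as the main result.

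**Conclusion.** The point holds conditionally and is a low-cost improvement. It needs a slope that is linear in time, a response that differs between participants, and more than half of that response present by week 2. Type I error is then about 6% to 9% for week 2 versus baseline and for the weeks 2/4 average versus baseline, under the assumed variances and a share of 70% to 100% by week 2. The documents give no variance components, so these figures illustrate the size and do not estimate it. The exact result for week 4 versus baseline assumes complete data. The quadratic terms need a statement of how time is coded; they are not an error under every reading.

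**What to change.** In Protocol 6b and the SAP, enter time as a three-level factor, which already covers the quadratic. Replace the random intercept and slope with an unstructured within-person covariance for the three visits and Kenward-Roger degrees of freedom. Name week 4 versus baseline as the primary contrast, in line with Protocol 5.6 (Cross-over design).

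The cost is a sentence or two in each document and two more covariance parameters (six against four), which is small with 60 to 120 participants. The unstructured form contains the planned structure as a special case, so nothing is misspecified if individual response does grow linearly.

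### The mixed model treats week-0 activity as an outcome rather than conditioning on it, so the treatment contrast is unbiased but less precise than the collected data allow

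*Protocol*

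**What the plan says.** Protocol section 6b lists both primary outcomes (daily steps and sedentary time) and the other accelerometer outcomes at "Week 0 (baseline); Week 2; Week 4". Changes "over time (3-time points) are analyzed using linear mixed effect models to account for the correlated data", with a random intercept and slope for each subject "as well as a group (2) x time (3) interaction fixed effect". Week 0 is thus one of the three response times, and nothing sets the arms equal there.

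The same section names a second analysis for the main hypothesis: "repeated measures ANCOVAs (with group as a between-subject factor and pre-post session as a within-subject factor". Despite the name, the pre value is again a level of the within-subject factor, not a covariate.

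Under Aim 1 the SAP also specifies linear mixed models, without a time structure. Its adjustment reads "Demographic variables (age, sex, socioeconomic status, neighborhood walkability) and AD multimodal risk score will be included as covariates of non-interest". Baseline activity is not listed. Section 6b does compare baseline sedentary time between groups to look for confounding, but commits to no adjustment for it.

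**The concern.** When baseline is a response and the group x time term is unconstrained, the treatment effect is a difference in change. Under the usual conditions that contrast has larger variance than one conditioning on baseline, and it over-corrects a chance imbalance at week 0.

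The covariates raise a related point. A subject-level covariate entered as a main effect moves all three weeks equally and so drops out of a within-person contrast. The AD-risk classification that stratifies randomisation (section 4.2) would then not sharpen the treatment estimate, although the result would be described as adjusted. What is at stake is precision on both primary outcomes, at a sample size with little to spare.

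**Working it through.** **1. The plan's own figure.** SAP inputs: difference 10%, SD 14%, two-sided alpha 0.05, power 80%, 30 per arm.
- Normal approximation: n per arm = 2 x (14 x (1.960 + 0.842)/10)^2 = 30.8, so 31. At 30 per arm power is 79.0%.
- Noncentral t: 32 per arm are needed; at 30 per arm power is 77.6%.

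The SAP figure is reproduced to within rounding. The SAP does not say whether 14% is the SD of change or of a single week's value, so both readings are carried.

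**2. What the mixed model estimates.** Simulated complete data were used: 30 per arm, three times, random intercept and slope, four prognostic subject-level covariates. Fitting was by generalised least squares with known covariance.
- Week-4 group x time contrast: 3.7131. Raw difference in mean change: 3.7131.
- With the four covariates added as main effects: 3.7131, SE 2.921 both ways.
- Over 60 REML fits, the estimates with and without covariates agreed to within 1e-13; mean SE was 2.872 without and 2.875 with.
- With about 15% of week 4 missing: estimate 3.198 without and 3.154 with covariates, SE 3.022 both ways.
- With the baseline means constrained equal and no covariates: SE 2.727 instead of 2.921.

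**3. Size of the loss.** With equal variance s^2 at each time and equal expected baseline means, the per-person variances are:
- change: 2 s^2 (1 - rho)
- baseline-adjusted: s^2 (1 - rho^2)
- ratio: (1 - rho^2) / [2(1 - rho)] = (1 + rho)/2

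Rho is an assumption. Power at 30 per arm (noncentral t, ignoring the degree of freedom spent on baseline):

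| rho | variance ratio | 14% = SD of change: change / adjusted | 14% = single-week SD: change / adjusted |
|---|---|---|---|
| 0.3 | 0.65 | 77.6% / 92.1% | 63.3% / 81.4% |
| 0.5 | 0.75 | 77.6% / 88.1% | 77.6% / 88.1% |
| 0.7 | 0.85 | 77.6% / 83.9% | 94.0% / 96.8% |
| 0.8 | 0.90 | 77.6% / 81.8% | 99.0% / 99.5% |
| 0.9 | 0.95 | 77.6% / 79.7% | near 100% for both |

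Example: at rho 0.7 with 14% the SD of change, the adjusted SD is 14 x sqrt(0.85) = 12.91. With 14% a single-week SD, the change SD is 14 x sqrt(0.6) = 10.84 and the adjusted SD is 14 x sqrt(0.51) = 10.00.

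**4. The other sample size.** The Protocol (Executive Summary and section 4.1) plans 120, or 60 per arm. With 14% the SD of change, unadjusted power is 97.3%, and adjustment gives 99.4% to 97.8% for rho 0.5 to 0.9. With 14% a single-week SD and rho 0.3, it is about 91% against 98%.

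**The case against.** **The Executive Summary defines the primary outcome as change from baseline, and the model estimates that.** True. Under randomisation the change contrast is unbiased and alpha is not inflated. A reader might infer that the effect estimate is invalid; nothing in the documents supports that.

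**Ineffective covariates are an inference.** This stands in part. No text says that covariates enter as main effects only; that is the natural reading of "AD multimodal risk score will be included as covariates of non-interest", and the claim joins the SAP's list to the Protocol's model. A reader might go further and conclude that the covariates cannot reach the treatment effect in either analysis. That fails for the repeated-measures ANCOVA: in its usual multivariate form, between-subject covariates act on the pre-post contrast too. In the mixed model the result is exact only for complete data.

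**The loss may be trivial.** It can be: at high rho, or with 120 participants, little is gained. A reader who looked only at low rho and 30 per arm would overstate the cost.

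**Baseline accelerometry follows randomisation.** The Research Activities text under section 4.2 places allocation before baseline assessment, and section 5.5 places the baseline accelerometer week between T1 and T2. A reader might infer that the gain holds whatever the timing, and that is too strong. If allocation shifts baseline alone by delta, change carries all of delta and the adjusted model only beta x delta, with beta, the baseline slope, below 1. If early dropout leaves a stable between-arm difference delta, change removes it and adjustment leaves (1 - beta) x delta. Neither estimator is better in both cases.

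**Conclusion.** The point holds as one of efficiency. The section 6b mixed model yields a raw difference in change, and conditioning on the week-0 value would lower its variance by 10% to 25% for rho 0.8 to 0.5. At the SAP's 60 participants, with 14% as the SD of change, unadjusted power falls a little short of the stated 80%, and adjustment brings it above 80% for rho up to 0.8. If the Protocol's 120 is the real target, the gain is small under most assumptions.

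This rests on equal variances over time, equal expected baseline means and an assumed rho. The covariate point is conditional on main-effects-only entry in the mixed model and on near-complete data. It is a change worth making, but not a threat to validity.

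**What to change.** For the accelerometer outcomes (steps, sedentary time, moderate-to-vigorous activity, cadence, bouts), specify one of:

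- **Baseline as covariate.** Responses at weeks 2 and 4; fixed effects for arm, week, arm x week, own baseline value, baseline x week, AD-risk stratum and the SAP covariates.
- **Common baseline mean.** Keep all three times, constrain the arms to one week-0 mean, and add covariate x time terms. This preserves the quadratic trajectory planned in section 6b.

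The week-2 and week-4 form cannot be copied to every outcome. Section 6b puts the neuropsychological tests at weeks 0, 1 and 4; sections 5.4 and 5.5 describe estimated fitness before and after only, and physical tests at T1, T3 and T4. For outcomes measured only before and after, use ANCOVA of the post value on the baseline value at their own scheduled times.

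Because baseline accelerometry follows randomisation, also report the change-score contrast as a sensitivity analysis. State whether 14% is the SD of change or of a single week, and reconcile 60 with 120.

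Cost: wording in the SAP and section 6b, a few degrees of freedom, and reliance on comparable baseline means between arms. No new data are needed.
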